## Protocol

**Title:** Barbed Suture: A Look at its Use for Hysterotomy Closure During Cesarean Sections

**Principal Investigator:** [name]

**Institution:** Icahn School of Medicine at Mount Sinai Hospital

[figure not shown]
**Background:** Surgical knot tying is a central part of any procedure and a crucial part of surgical technique. However, while it is a means of tissue approximation, more importantly, knot tying plays a role in anchoring the suture to the tissue. Knot tying also introduces human error and interuser variability given the innate differences in ability to tie a secure knot (1). Barbed suture has pioneered the way for knot-less surgical technique, thereby decreasing some of the human error associated with the process of tying a knot. Bidirectional barbed suture incorporates tiny barbs that distribute the tension along the entire suture line rather than the knotted ends as seen with traditional suture material (2). With barbed suture, no knots are required. There have been several studies looking at the use of barbed suture in gynecology and it is already in wide use in the field of minimally invasive gynecological surgery, however very few studies have looked at the use in obstetrics. Currently cesarean sections are the most common procedure performed in the United States (6) and at our institution we perform over 8,000 deliveries per year. The objective of this study is to investigate whether barbed suture conveys a decrease in quantitative blood loss when compared to conventional suture.

**General Design:** This is a prospective, randomized controlled trial evaluating whether using a barbed suture to close a C-section incision can reduce blood loss. Patients undergoing C-section will be randomized with equal allocation to a barbed suture or a standard antimicrobial suture. The primary outcome is quantification of blood loss (QBL). At Mount Sinai Hospital, QBL is calculated by Triton AI which captures sponge and canister images to accurately monitor blood loss in real time. Differences between the groups will be assessed using a 0.05 level Wilcoxon rank-sum test. Secondary outcomes include time for hysterotomy closure, need for additional hemostatic sutures, rate of endometritis/SSI (superficial wound infection, deep wound infection, and endometritis) within 6 weeks postpartum, use of hemostatic agents, and differences in pain which will be assessed by a telephone screening in the days following delivery. The Mann-Whitney test will be used to compare continuous outcomes between the barbed suture and antimicrobial suture groups. Continuous secondary outcomes include time for hysterotomy closure (in minutes), and difference in pain between post-surgery day 1 and day 14. The Chi-square test or Fisher's exact test (as appropriate) will be used to compare the incidence rate of binary outcomes between the two patient groups. Binary secondary outcomes include need for additional hemostatic sutures (Y/N), endometritis or surgical site infection (SSI) within 6 weeks of surgery (Y/N), and use of hemostatic agents (Y/N). **Inclusion criteria** (1) those undergoing an elective scheduled cesarean delivery at  $\geq 37$  weeks' gestation, (2) those in labor requiring cesarean delivery for usual obstetrical indications, or (3) those who failed a trial of labor after a previous cesarean delivery at Mount Sinai Hospital ages 18-64. **Exclusion criteria include**, multifetal gestations, placenta previas, and patients with a known coagulopathy (DIC, Von Willebrands Disease, etc). Also excluded are patients with IAI, patients on magnesium sulfate, placenta abruption, and PAS.

**Sample Size:** Sample size is based on a two-sided, equal variance T-test. Since the distribution of QBL is non-normal, the calculation was inflated by 15% to ensure adequate power for the nonparametric Wilcoxon rank-sum test as recommended by Lehmann (5). Based on data from C-section patients seen at Mount Sinai from 2018-2019, the distribution of QBL is assumed to have a mean of 534 and a standard deviation of 371. (Figure 1).

*Figure 1. Distribution of QBL in C-Section Patients at Mount Sinai from 2018-2019*

Assuming each group has a standard deviation of 371 and the control group has a mean QBL of 534, a sample size of 226 patients (113 in each group) provides ~85% power to detect a 30% decrease in mean QBL between the groups at the 0.05 significance level. Sample size for alternative effect sizes are tabled below. 300 sutures are requested by the investigators to standardize a double layer closure for all patients as is the standard of care for most Obstetricians (113 patients in the barbed suture arm, double layer would require 226 suture, we are requesting 452 suture so extra suture is available should additional hemostatic sutures be needed.

Power	Alpha	Mean QBL in Control Group	Mean QBL in Experimental Group	Standard Deviation in Both Groups	Absolute Difference of Means	Relative Difference of Means	Group N	Total N
0.85	0.05	534	267	371	267	50%	42	84
0.85	0.05	534	320.4	371	213.6	40%	65	130
0.85	0.05	534	373.8	371	160.2	30%	113	226
0.85	0.05	534	427.2	371	106.8	20%	251	502

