### **Benefits**

There is no direct benefit.

The benefit to society is that since barbed suture is successfully and routinely used in gynecological surgery, establishing its use in obstetrical surgery could demonstrate improvements in patient care in the form of shorter operative times, more secure tissue approximation without the introduced interuser variability due to knot tying, and decreased risk of infection and pain. As cesarean sections are the most common procedure being performed in the U.S, any advances in surgical technique would prove extremely useful.

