### **Scientific rationale for study designer**

This study is extremely feasible given 1/3 of all 8,000 deliveries performed at Mount Sinai are cesarean sections.

This is a prospective, randomized controlled trial evaluating whether using a barbed suture to close a C-section incision can reduce blood loss. Patients undergoing C-section will be randomized with equal allocation to a barbed suture or a standard antimicrobial suture. The primary outcome is quantification of blood loss (QBL). Differences between the groups will be assessed using a 0.05 level Wilcoxon rank-sum test. Secondary outcomes include time for hysterotomy closure, need for additional hemostatic sutures, rate of endometritis, use of hemostatic agents, and differences in pain which will be assessed by a telephone screening 2 weeks following delivery. The patients will be contacted by study personnel 2 weeks after delivery (they will be instructed on this upon discharge) to discuss pain control, bowel or bladder complaints, and amount of narcotic use necessitated post-operatively. Demographic information will be obtained from the electronic medical record.

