#### **Product storage and preparation**

The device will be stored in the locked office of one of the research personnel and will only be handles by the research team until randomization is performed and the patient is allocated to the treatment arm. Only at that time would the research personnel go into the locked office and obtain the suture material for the subject. The material would be then handed off with sterility to the scrub tech who would provide the suture to the surgeon during the procedure

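### The only pain analysis given a test compares the day 1 to day 14 change, both after suture placement, so it can hide or reverse a real pain benefit of barbed suture

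*Combined protocol and SAP*

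**What the plan says.** The General Design paragraph lists two continuous secondary outcomes. One is hysterotomy closure time and the other is the "difference in pain between post-surgery day 1 and day 14". The test follows from the sentence "The Mann-Whitney test will be used to compare continuous outcomes between the barbed suture and antimicrobial suture groups". No other pain variable is given a form or a test anywhere in the document.

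The timing of collection is described in two ways. General Design has "differences in pain which will be assessed by a telephone screening in the days following delivery". The section Scientific rationale for study designer has "differences in pain which will be assessed by a telephone screening 2 weeks following delivery", and adds "The patients will be contacted by study personnel 2 weeks after delivery". Neither explicitly schedules a score on day 1.

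No pain scale, direction of subtraction or pre-operative pain score is given. The Benefits section names "decreased risk of infection and pain" among the improvements the trial might demonstrate.

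**The concern.** Read as a within-patient change, which is the most natural reading, the variable uses day 1 as the reference from which recovery is measured. That would be sound if day 1 came before the intervention. It does not: Product storage and preparation has the scrub tech "provide the suture to the surgeon during the procedure". Pain on day 1 can therefore already differ between arms because of the suture, and subtracting one day from the other removes whatever part of the effect the two days share.

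The quantity tested is then how fast pain falls after day 1, not whether patients hurt less. A suture that reduces pain mainly in the first days leaves less room for a later fall and would score worse. Since less pain is one of the stated hopes for barbed suture, the trial could report no pain effect, or an adverse one, when patients in that arm had less pain.

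**Working it through.** **The plan's own figure.** There is none for pain. The arm size used below is the one in the Sample Size section. A two-sided t-test with difference 160.2, SD 371, alpha 0.05 and power 0.85 needs 97.3 per group, rounded up to 98. Then 98 × 1.15 = 112.7, rounded up to 113, or 226 in all, which matches the plan.

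**Algebra, free of assumptions about scale, SD or sample size.** Let C1 and C14 be the control means on the two days. Let b1 and b14 be the reductions in mean pain with barbed suture.

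- Fall in control = C1 − C14
- Fall with barbed = (C1 − b1) − (C14 − b14)
- Contrast (barbed minus control) = b14 − b1

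The contrast is negative when b1 > b14, zero when b1 = b14, and positive only when b14 > b1. For example, take control means of 5.5 and 2.5 with benefits of 1 and 0.5. Control falls by 3.0, and barbed goes from 4.5 to 2.0, a fall of 2.5. Barbed suture is better on both days, yet its fall is 0.5 smaller.

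**Size under assumed inputs.** From the documents: equal allocation, 113 per arm, Mann-Whitney test. Assumed: a two-sided 0.05 level for this secondary test; a 0–10 scale with scores rounded and clipped to that range; control means 5.5 and 2.5; SDs 2.2 (day 1) and 1.8 (day 14); correlation 0.3, 0.45 or 0.6. There were 4,000 simulated trials per scenario. Entries are percentages of trials significant at correlation 0.3 / 0.45 / 0.6, with a larger fall read as better.

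| Benefit day 1, day 14 | Planned change test | Direct day 1 test | Direct day 14 test |
|---|---|---|---|
| 0.3, 0 | 16.0 / 17.1 / 21.9 against barbed | | |
| 0.5, 0 | 33.3 / 39.8 / 49.8 against | | |
| 1, 0 | 87.0 / 92.8 / 97.5 against | | |
| 1, 0.5 | 39.9 / 45.9 / 56.9 against | | |
| 0.5, 0.5 | 4.9 / 5.5 / 5.4 either way | 36.2 / 36.2 / 38.7 | 50.0 / 51.9 / 51.1 |
| 1, 1 | 6.3 / 7.2 / 7.9 either way | 90.9 / 92.0 / 91.3 | 97.9 / 98.0 / 97.7 |
| 0.5, 1 | 20.6 / 25.2 / 31.1 in favour | | 97.5 / 97.7 / 97.8 |
| 0, 0 | 4.8 / 4.5 / 5.1 either way | | |

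Blank cells are not needed for the argument.

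**Hand check of the 1, 0 row.** The SD of the change is √(2.2² + 1.8² − 2ρ × 2.2 × 1.8), which is 2.39 at ρ = 0.3 and 1.82 at ρ = 0.6. The standard error of the contrast is that SD times √(2/113) = 0.133, giving 0.318 and 0.243. A 1-point contrast is then 3.15 or 4.12 standard errors. A normal approximation for a comparison of means puts the chance of significance at about 88% and 98%, in line with the simulated 87.0% and 97.5%.

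**Sensitivity** (3,000 trials each, correlation 0.3 / 0.6, significant against barbed suture):

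| Setting | 0.3, 0 | 0.5, 0 | 1, 0 |
|---|---|---|---|
| 20% loss, 90 per arm | 12.6 / 18.2 | 30.0 / 40.9 | 77.2 / 93.2 |
| SDs 2.5 and 2.0, 113 per arm | 13.3 / 18.4 | 26.3 / 41.9 | 78.2 / 93.1 |

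A separate simulation with unclipped normal scores, SD 2 on both days and correlation 0.3 to 0.7 (1,000 trials each) gave the same picture. Equal 1-point benefits were significant in 4–5% of trials, against 94–96% for the direct tests. Benefits of 1 and 0.5 went against barbed suture in 35–65%.

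**The case against.** The strongest reply concerns reading. The outcome lists are introduced as inclusive rather than complete, and the 2-week telephone contact in the rationale section could be taken as a between-arm comparison at about day 14. The quoted phrase might also mean an arm difference over the day 1 to day 14 window. It is fair to say that a single-day comparison is not ruled out. But none is given a variable or a test, and choosing one after the data are seen would be open to selective reporting. If separate comparisons were intended, the text needs to say so.

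Second, the documents never say that a larger fall is better. That stands, and the finding against barbed suture is conditional on it. With the sign read the other way, a larger day 14 benefit would count against barbed suture, and equal benefits would still show nothing. Neither direction measures whether pain is reduced. An analyst holding both scores could notice that a smaller fall came from a lower day 1 score, but the plan does not ask for that check.

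Third, every rate rests on assumed pain values. This also stands. Small effects do little harm: a day-1-only benefit of 0.1 point gives about 4–6% against barbed suture, and 0.2 gives about 8–12%. The 6–8% in the equal 1-point case, rather than 5%, arises because clipping at 0 shrinks the observed day 14 benefit to about 0.87, against 0.98 on day 1.

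Last, change between two post-operative days is a legitimate description of recovery. As the sole tested measure of pain, it is not adequate.

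**Conclusion.** The concern holds. As written, the pain analysis tests the day 14 benefit minus the day 1 benefit. It therefore misses a benefit that is equal on both days and, if a larger fall is read as better, goes against barbed suture when the benefit is mainly early.

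The sign result rests only on the within-patient reading and the stated direction. The rates depend on the assumed scale, SDs and correlation. Over the settings tried with 113 per arm and the main SDs, an early-only benefit of 0.5 to 1 point turns significant against barbed suture in 33–98% of trials. When the day 14 benefit is the larger (0.5 then 1), the change test points the right way but detects it in only 21–31%, against about 98% for a direct day 14 test.

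This should be fixed, but it is limited to one secondary outcome.

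**What to change.** Replace the change outcome with between-arm comparisons of the pain score itself at day 1 and at day 14. Use a Mann-Whitney test at each day, or one repeated-measures model reporting the arm difference at each day. Name the pain scale. If the day 1 to day 14 change is kept, report it as a description of recovery, with the direction of subtraction stated and no claim of benefit attached.

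Reconcile General Design with Scientific rationale for study designer so that each score is collected on the day it refers to and the day 1 score does not depend on recall at 2 weeks.

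The cost is a wording change, one additional secondary test, and one early pain score if it is not already collected. The current outcome needs that early score anyway. The sample size does not change.

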### **Provisions to decrease risk**

This study is greater than minimal risk, however there are no reasonably foreseeable risks to the subjects and no inconvenience as they are recruited/screened/consented during their routine prenatal care. The barbed suture is not being used outside of its scope of use. There is always a risk of breach of confidentiality.

Patients will be recruited by their obstetrical provider. To mitigate the risk of breach of confidentiality and ensure confidentiality, the following system will be adhered to: when subjects are enrolled in this study, they will be assigned a unique identification code.

Corresponding medical record numbers for each code (keycode will be stored in a password locked documentation the MFM servers that can be accessed only by members of the research team. At the conclusion of the data extraction, the outcome variable will be assessed and the key codes to the medical record number will no longer be necessary, and that information will be permanently erased from the key code file. Electronic data with identifiers will be encrypted according to Data Security Standards.

### **Benefits**

There is no direct benefit.

The benefit to society is that since barbed suture is successfully and routinely used in gynecological surgery, establishing its use in obstetrical surgery could demonstrate improvements in patient care in the form of shorter operative times, more secure tissue approximation without the introduced interuser variability due to knot tying, and decreased risk of infection and pain. As cesarean sections are the most common procedure being performed in the U.S, any advances in surgical technique would prove extremely useful.

### **Risk/benefit assessment**

This research involves less than minimal risk. To mitigate the risk of breach of confidentiality and ensure confidentiality, the following system will be adhered to: when subjects are enrolled in this study, they will be assigned a unique identification code. Corresponding medical record numbers for each code (keycode will be stored in a password locked documentation the MFM servers that can be accessed only by members of the research team. At the conclusion of the data extraction, the outcome variable will be assessed and the key codes to the medical record number will no longer be necessary, and that information will be permanently erased from the key code file. Electronic data with identifiers will be encrypted according to Data Security Standards.

Data analysis will be performed at the halfway mark to ensure there is no inadvertent harm to the subjects. Additionally, the barbed suture will be used in the capacity of its labeled use. Therefore the potential risk to the subject is low. There is no risk to the fetus as it will be delivered prior to the intervention

There is no direct benefit.

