#### **Safety assessments**

This research involves less than minimal risk. To mitigate the risk of breach of confidentiality and ensure confidentiality, the following system will be adhered to: when subjects are enrolled in this study, they will be assigned a unique identification code. Corresponding medical record numbers for each code (keycode will be stored in a password locked documentation the MFM servers that can be accessed only by members of the research team. At the conclusion of the data extraction, the outcome variable will be assessed and the key codes to the medical record number will no longer be necessary and that information will be permanently erased from the key code file. Electronic data with identifiers will be encrypted according to Data Security Standards.

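### Does the halfway harm analysis mean that the final 0.05 test on blood loss must be adjusted?

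*Combined protocol and SAP*

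**What the plan says.** The halfway look appears once, in Risk/benefit assessment: "Data analysis will be performed at the halfway mark to ensure there is no inadvertent harm to the subjects". The sentence does not say which outcomes are used, whether arms are compared, who sees the results, or what would follow from them.

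General Design, repeated under the scientific rationale, sets the primary analysis of QBL: "Differences between the groups will be assessed using a 0.05 level Wilcoxon rank-sum test". The Sample Size paragraph uses the same level for a single analysis: "Sample size is based on a two-sided, equal variance T-test", and "a sample size of 226 patients (113 in each group) provides ~85% power" for a 30% fall in mean QBL. None of these places mentions the halfway look.

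The Safety assessments section, where detail on the look might be expected, holds confidentiality text and the statement "This research involves less than minimal risk". Provisions to decrease risk says the opposite: "This study is greater than minimal risk, however there are no reasonably foreseeable risks to the subjects".

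**The concern.** Looking at accumating data and then testing at the full level is the standard route to an inflated false-positive rate. Greater blood loss is a natural harm measure here and is also the primary outcome. The only primary test and level in the plan are the Wilcoxon rank-sum test at 0.05. A reader could therefore suppose that this test is run at both looks without a boundary, in which case the stated 0.05 would not hold.

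There are two further worries. A nominal 0.05 harm test halfway carries a 2.5% chance of a false harm signal. Interim results by arm might also reach staff who consent patients or handle the sutures, because no reviewer is named and no blinding is described.

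**Working it through.** **Inputs.** From Sample Size: control mean 534 and SD 371 in each arm, difference 160.2 (30% of 534), two-sided 0.05, power 0.85, 15% inflation for the rank test, 113 per arm. From Risk/benefit assessment: one look at half the patients, so 226/2 = 113 in total, or about 56 per arm.

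**1. The plan's sample size.** Normal approximation: n = 2 × [371 × (1.960 + 1.036)/160.2]² = 96.3, so 97 per arm. The t-test version gives 98, and 98 × 1.15 = 112.7, so 113 per arm. The stated figure reproduces, and it is sized for one analysis at 0.05.

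**2. Worst case: two-sided 0.05 at both looks.** Under the null, the test statistics Z1 (halfway) and Z2 (final) are approximately bivariate normal with correlation √0.5.

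- P(|Z1|>1.96 or |Z2|>1.96) = 0.05 + 0.05 − 0.0169 = 0.0831.
- A simulation of the Wilcoxon test (40,000 null trials, lognormal QBL with mean 534 and SD 371, 56 then 113 per arm) gave 0.0829 for the two looks and 0.0501 for the final test alone.

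**3. Harm-only look, benefit claimed only at the end.** Let positive Z favour barbed suture, and suppose the trial stops halfway if Z1 < −1.96.

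- False benefit: P(Z1 > −1.96 and Z2 > 1.96) = 0.0250 to four decimals. Stopping for harm can only remove such claims.
- Any false rejection: 0.025 + 0.05 − 0.0084 = 0.0666. Of this, 0.0250 is benefit and 0.0666 − 0.0250 = 0.0416 is harm. The whole excess lies in the harm direction, and it arises only if a formal one-sided 0.025 stopping test is used, which the plan does not contain.

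**4. Would a p<0.001 harm threshold be better?** With that boundary halfway and 0.05 at the end, the overall level is 0.0502. The cost falls on the ability to see harm. For a rise of 160.2 with 56 per arm, the expected Z is 160.2/(371 × √(2/56)) = 2.285. With rank-test efficiency taken as 1/1.15, it is 2.285/√1.15 = 2.131.

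| Two-sided threshold | Critical value | Power, efficiency 1/1.15 | Power, efficiency 1 |
|---|---|---|---|
| 0.05 | 1.960 | Φ(0.171) = 0.57 | Φ(0.325) = 0.63 |
| 0.001 | 3.291 | Φ(−1.160) = 0.12 | Φ(−1.006) = 0.16 |

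**5. If stopping for benefit were intended.** O'Brien-Fleming nominal levels would be 0.0052 halfway and 0.0480 at the end. Power of the final test alone, on the normal approximation with 113/1.15 per arm, moves from 0.857 to 0.853.

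**The case for a change.** The strongest case for acting is that a stated purpose is not a rule. Harm from a suture can hardly be judged without comparing arms, QBL is an obvious measure, and no sentence forbids an early claim if halfway data favour barbed suture. The error rate of an unspecified look cannot be read off the plan, and a paragraph of wording would settle it at almost no cost in power.

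Part of this stands. The look is underdescribed, and a comparison by arm is the likely reading, though a descriptive review of event counts would also fit the sentence. The arithmetic for two looks is correct under its assumptions.

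The rest goes further than the text. No section says that QBL is tested halfway at 0.05, or provides for stopping for benefit. The look is not without harm outcomes: General Design lists additional hemostatic sutures, hemostatic agents and infection within 6 weeks, and the scientific rationale adds bowel or bladder complaints and narcotic use. That staff would see results by arm is conjecture, because no section says who sees the analysis. Product storage and preparation shows only that research personnel fetch the allocated suture. The conflicting risk labels are a slip in the ethics wording; they deserve tidying but affect no error rate or estimate.

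**Conclusion.** No change to the statistical plan follows. As written, the look is for harm, and on that reading the error that would mislead the trial's main conclusion, a false claim of reduced blood loss, stays at 2.5%. The 8.3% is a worst case that needs three things the documents do not state: the QBL test run halfway, the 0.05 level applied to it, and an early benefit rejection counted as a positive result.

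The possible remedies bring little. Naming outcomes and a reviewer records detail that an analyst would supply sensibly. A group-sequential boundary guards against a benefit stop that is not planned. The p<0.001 threshold protects an overall level that matters little for a safety check, and cuts the chance of flagging a 30% rise in QBL from 57–63% to 12–16%; that is a debatable trade-off and not a correction.

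This conclusion assumes that benefit is claimed only at the final analysis. If the team did intend to stop early for benefit, a boundary would be needed, and the O'Brien-Fleming levels in the working show that it would cost about 0.4 points of final-test power.
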